9.7.4 Statistical Considerations

Statistical assumptions

The above are rough, very first estimates based on several assumptions. Interim analyses will take place in order to verify that these assumptions (e.g. in Table 1) were accurate and consider the need for potential adjustments.

Sensitivity analyses

Variations in the PPV will be explored in order to allow for potential errors in the estimates and assumptions used.

9.8 Quality Control

9.8.1 Validation

Validation of vaccination history will be done by PHE.

Due to the severity of meningococcal disease we assume that most cases of *Neisseria meningitidis* are being captured by the national surveillance system. Capsular group confirmation is estimated to be available for more than 90% of confirmed cases, of which 50-60% are confirmed by PCR only (PHE, personal communication). Subsequent evaluation of 4CMenB specific antigens using MATS on culture-positive isolates will be done for part of all notified cases.

9.8.2 Record Retention

NA. The study in this protocol refers to the provision of customised post-marketing surveillance reports of independently generated data to assist GSK Vaccines S.r.l. in meeting its regulatory commitment.. Records retention falls within PHE routine practices for surveillance data.

9.9 Limitations of the Research Methods

Reporting of meningococcal cases is based on passive surveillance which may be an underestimate of true disease. Additionally, the national surveillance system may not capture data from meningococcal patients that died from the disease. However, as meningococcal disease is a serious illness, we expect that not many cases will be missed and that even from deaths samples will be available for diagnostic confirmation of IMD. The main benefit of using national surveillance data is that the results may be generalisable to the whole UK population and potentially even beyond its borders.

GSK Vaccines S.r.l.		Observational Study Protocol V72_38OB
03 SEP 15 Version 3 Final	Confidential	Page 44 of 61

For the screening method, aggregated data will be used. The 'cost' of the simplicity is that no control for confounding is possible. However, in a NIP this should not be an issue. Also, the screening method provides a quick and proven design to perform this study.

The study may run into feasibility issues due to lack of precision of estimates, especially with high coverage and/or low vaccine effectiveness. Additionally, meningococcal disease has declined during the past decade in England and Wales.

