9.4 Data Sources

Exposure of interest

Data for this study will be collected through the national surveillance system, as well as an additional source(s) to collect data regarding vaccinations. All cases of confirmed MenB disease will routinely be followed up to obtain vaccination history (including batch number) through enhanced surveillance by PHE. Additionally, demographics and medical history will be ascertained.

For the analytical study the screening method will be used. As above, vaccine history of confirmed cases will be collected to assess the proportion of cases that were fully vaccinated (PCV).

The comparator will be national vaccination rates as the proportion population vaccinated (PPV). These data may for instance be taken from the Cover Of Vaccination Evaluated Rapidly (COVER) system which collects data about the coverage of routine infant vaccination from health authorities in England, and/or from a general practice database [Anon, 1999]. COVER data would have some limitations as it only provides coverage at fixed time points (12, 24 months) and we would not know about partial vaccination. Data will therefore be supplemented by disaggregate data obtained from either general practice or child health database to provide estimates of dose specific coverage at specific ages.

Outcomes of interest

The study will be partnered with Public Health England (PHE) and its Meningococcal Reference Unit (MRU) in England, so that national laboratory surveillance data for meningococcal disease can be used [Gray SJ et al., 2006]. PHE's national surveillance system consists of statutory reporting of confirmed invasive meningococcal disease by laboratories. Statutory notification by physicians to local units of PHE ensures rapid follow up of clinically diagnosed cases and helps to ensure complete laboratory investigation. Clinical specimens and isolates of *Neisseria meningitidis* are also referred for capsular group specific PCR and routine serogrouping and subtyping.

In addition, all isolates referred to MRU from individuals eligible for vaccination will have qualitative and quantitative assessment of meningococcal antigens (Meningococcal antigen typing system or MATS) will be evaluated for each case where the organism is identified by culture. For cases with PCR-only confirmation of capsular group B (no

GSK Vaccines S.r.l.		Observational Study Protocol V72_38OB
03 SEP 15 Version 3 Final	Confidential	Page 31 of 61

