9.5 Study Size

a. Screening method

The number of cases required to estimate vaccine effectiveness with various levels of precision (based on the difference between the point estimate of VE and lower limit of the 95%CI) is shown in Table 1 below [Farrington CP, 1993]. Calculations assume 90% vaccine coverage in the populations and consider observed VE for 50% to 80%.

Table 1	Screening Method (Sample Size Calculation)
---------	--

Vaccine Coverage	Lower 95% CI limit below VE	Vaccine Effectiveness 50%	Vaccine Effectiveness 60%	Vaccine Effectiveness 70%	Vaccine Effectiveness 80%
	5%	3022	1742	882	361
90%	10%	874	516	271	117
2070	15%	445	269	145	65
	20%	284	175	97	45

If we assume 90% vaccine coverage and observe 60% vaccine effectiveness, then with 175 cases, the lower limit of the 95% confidence interval (CI) for vaccine effectiveness will be above 40%.

b. Case-control method

The number of cases and controls required (1:3 ratio) to estimate vaccine effectiveness with various levels of precision (based on the difference between the point estimate of VE and lower limit of the 95%CI) is shown in Table 2 below. The calculations assume 90%

GSK Vaccines S.r.l.		Observational Study Protocol V72_38OB
03 SEP 15 Version 3 Final	Confidential	Page 35 of 61

of controls are exposed to vaccine and consider observed VE for 50% to 80% [Schesselman JJ, 1982a], [Schesselman JJ, 1982b].

Table 2	Case-control Method (Sample Size Calculation for 1:3 matching)				
Probability of vaccination in controls	Lower 95% CI limit below VE	Vaccine Effectiveness 50%	Vaccine Effectiveness 60%	Vaccine Effectiveness 70%	Vaccine Effectiveness 80%
	5%	4900	2820	1428	585
90%	10%	1400	835	440	190
2070	15%	720	435	235	105
	20%	460	284	157	73

If we assume a vaccine exposure rate in the control population of 90% and observe 60% vaccine effectiveness, then with 284 cases and 852 controls (1:3 matching), the lower limit of the 95% confidence interval for vaccine effectiveness will be above 40%.

[figure not shown]
Expected numbers and feasibility

In order to calculate the expected number of cases after introduction of the 4CMenB vaccine in the UK, we need to take the currently observed number of cases and the vaccination status by age group into account. Figure 6 shows an assumed vaccination schedule by birth cohort for the years 2013, 2014 and 2015.

GSK Vaccines S.r.l.		Observational Study Protocol V72_38OB
03 SEP 15 Version 3 Final	Confidential	Page 36 of 61

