9.7.3 Statistical Methods

For each of the proposed study designs, the statistical methods are as follows:

1. Descriptive (no hypothesis testing):

This study will provide a summary of the epidemiology of all capsular groups of meningococcal disease, e.g. by vaccination status, age, setting and method. The method will be purely descriptive and summarise the observed number of *N. meningitidis* cases reported to PHE, stratified by variable of interest. More details are described above.

2. Analytical study:

Vaccine effectiveness (VE) is generally defined as the % reduction in the attack rate in vaccinated compared with unvaccinated children in the same birth cohorts. VE will be assessed by the screening method, or by a case-control method if the screening method cannot be used (for example, if appropriate coverage data cannot be determined).

a. Screening method:

For this method, the VE can be estimated using the formula below, where PCV is the proportion of cases that are vaccinated and PPV is the proportion population vaccinated (coverage):

$$VE = 1 - (\underline{PCV \times (1-PPV)})$$
$$((1-PCV) \times PPV)$$

The vaccine effectiveness estimate will be calculated along with the 95% confidence interval using the exact binomial distribution for the proportion of cases vaccinated in each of the study settings.

b. Case-control method:

In case-control studies, vaccine effectiveness is based on the odds ratio (OR) and is defined as: VE = 1 - OR

The vaccine effectiveness estimate will be calculated along with the 95% confidence interval using the standard errors from logistic regression.

If it is decided to pursue a case-control method, for instance if uptake information is difficult to obtain, the three controls for each case would as a minimum be matched on age (same month of birth if that is sufficient to define vaccine eligibility for infants) and sex.

As mentioned earlier, additional calculations can be considered to investigate the doseresponse relationships for each antigen in the vaccine (versus having at least one antigen, as described in the secondary objective).

As the number of cases due to other capsular groups is expected to be too small for analysis within the study period, at a later stage, outside the scope of this study protocol, it could be envisioned to evaluate both cross protection against other capsular groups and any capsule replacement after introduction of the vaccine.

Subgroup analyses

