If sample size allows, stratified analyses may be performed.

Methods to control for confounding

For this study the screening method will be used, which is a relatively quick and easy way to assess vaccine effectiveness. The 'cost' of the simplicity is that no control for confounding is possible.

For the case-control method, odds ratios and 95% confidence intervals will be calculated by using a multivariate conditional logistic regression after matching by age, gender and calendar time (c-c ratio 1:3). Covariates will be included into the multivariate model if they are significantly (p<0.05) associated with meningitis and change the point estimate between 4CMenB vaccination and MenB disease at least 10%.

Stratified analyses will be conducted to estimate the effect by age, gender and in specific subgroups e.g. immunocompromised subjects, method of data collection (databases versus networks) and outcome (meningitis serotypes). For all analyses we will accept statistical significance at a p-value<0.05. Analyses will be performed by using the statistical software package SAS.

Methods to control for effect modification

In case of case-control method, Breslow-Day test for homogeneity of the odds ratios and inclusion of interaction term in the conditional logistic regression model will be used in order to investigate effect modification.

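### The protocol dismisses confounding in the screening method without support and does not tie each case to coverage at its age and birth cohort

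*Protocol*

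**What the plan says.** Section 9.7.3, under methods to control for confounding, says of the screening method: "The 'cost' of the simplicity is that no control for confounding is possible". Section 9.9 repeats this and adds the reassurance: "no control for confounding is possible. However, in a NIP this should not be an issue". Section 9.1, item 3, says something different: in this method control comes through external standardisation on a coverage figure taken from outside the study.

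Section 9.7.3 defines VE as the reduction in attack rate in "vaccinated compared with unvaccinated children in the same birth cohorts". It then gives one formula, VE = 1 - PCV(1 - PPV) / ((1 - PCV)PPV), with a 95% interval obtained "using the exact binomial distribution for the proportion of cases vaccinated in each of the study settings". PCV is the proportion of cases vaccinated and PPV the proportion of the population vaccinated.

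Section 9.4 notes that COVER reports coverage only at 12 and 24 months, and plans supplementary data giving dose-specific coverage at particular ages. Stratified analyses appear twice in section 9.7.3: once as optional if numbers allow, and once as a firm plan by age and gender, directly after the case-control paragraph. Section 9.7.4 plans to vary PPV, without a range. Section 9.2.3 excludes people not offered the vaccine and those partially vaccinated.

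**The concern.** A national programme does not remove confounding by age or birth cohort. In a programme being rolled out, a child's age and birth cohort determine which doses the child can have had, and age also drives disease risk. If cases of different ages are pooled and compared with a coverage figure that does not reflect their age mix, the screening formula returns a biased VE.

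The claim that nothing can be done is also too strong. The same formula, applied with coverage specific to age and cohort and then combined, controls those two factors, and section 9.4 already plans data by dose and age. As written, the protocol tells the analyst that adjustment is impossible and unnecessary, and leaves those data without a stated role in the estimate. The precision target is a lower limit 20 points below a VE of 60%, so a bias of 7 to 16 points would take up much of that margin.

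**Working it through.** **1. The plan's own figure.** Section 9.5 states: "If we assume 90% vaccine coverage and observe 60% vaccine effectiveness, then with 175 cases, the lower limit of the 95% confidence interval" for VE will lie above 40%. With PCV = PPV(1 - VE) / (1 - PPV x VE), PCV = 0.9 x 0.4 / (1 - 0.54) = 0.7826. At VE 40%, PCV = 0.54 / 0.64 = 0.84375. Then n = 1.96² x 0.7826 x 0.2174 / (0.84375 - 0.7826)² = 174.8, against 175 stated. All 16 cells of Table 1 reproduce this way. With the planned exact interval, 137 of 175 cases vaccinated gives VE 59.9% (41.0 to 72.2). The stated precision therefore holds if PPV is exactly 90%.

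**2. Sensitivity to PPV.** Holding PCV at 78.3%:

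| PPV used | VE |
|---|---|
| 85% | 36% |
| 88% | 51% |
| 90% | 60% |
| 92% | 69% |
| 95% | 81% |

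A 2-point error in PPV moves VE by about 9 points, and the binomial interval for PCV does not carry that error.

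**3. Age pooling.** Inputs from the protocol: 210, 119 and 51 cases at under 1, 1 and 2 years (Table 3), a ratio of 210/51 = 4.1. Section 9.5 places 5/12 of infant cases before 5 months, which leaves 210 x 7/12 = 122.5 at 5 to 11 months. Assumptions: true VE 60% in every stratum, equal population per month of age, and the coverage values below. The protocol itself gives only a flat 90%.

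Expected vaccinated cases are the sum of N x c x 0.4 and unvaccinated cases the sum of N x (1 - c), where N is the stratum's case count and c its coverage. Pooled PPV is the population mean of c.

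Example with 90% at 1 year and 80% at 2 years: vaccinated 42.84 + 16.32 = 59.16; unvaccinated 11.9 + 10.2 = 22.1; PPV 85%; VE = 1 - (59.16 / 22.1) x (0.15 / 0.85) = 52.8%.

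| Assumed coverage | Pooled VE |
|---|---|
| 90% at 5-11 months and at 1 year | 60.0% |
| 80% at 5-11 months, 90% at 1 year | 64.3% |
| 70% at 5-11 months, 90% at 1 year | 66.7% |
| 50% at 5-11 months, 90% at 1 year | 69.7% |
| 80% at 1 year, 90% at 2 years | 65.5% |
| 90% at 1 year, 80% at 2 years | 52.8% |
| 90 / 85 / 80% at 5-11 months / 1 / 2 years | 53.0% |
| Three doses: 0% under 1 year, 90% at 1 year | 76.4% |

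Last row: 1 - (42.84 / 221.9) x (0.55 / 0.45) = 76.4%. Other contrasts go further: 95 / 85 / 80% gives 48.0%, and 90% at 1 year with 50% at 2 years gives 39.2%. Logistic regression among cases with offset logit(PPV) by age returns 60.0% in every row.

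**4. Twelve-month coverage applied to younger infants.** Assume coverage of 75, 82, 86, 88, 89, 90 and 90% at ages 5 to 11 months, with incidence halving over that span. Using PPV = 90%, a true 60% is estimated as about 75.5% and a true 0% as about 39%. Using the simple mean coverage (85.7%), the estimates are 63% and 8%. Using incidence-weighted mean coverage (about 84.6%), they are 60.0% and 0.0%.

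**5. What matching cannot remove.** If unvaccinated children have 0.8, 1.2 or 1.5 times the baseline risk for reasons not captured in the coverage data (assumed), a true 60% appears as 1 - 0.4/0.8 = 50%, 1 - 0.4/1.2 = 67% or 1 - 0.4/1.5 = 73%.

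**The case against.** The best defence is that section 9.7.3 gives the generic screening formula and does not commit to one PPV for all cases. VE is defined within birth cohorts, section 9.5 looks for conclusions in each age group, age-specific coverage is planned, stratification and PPV variation are mentioned, and people not offered the vaccine are excluded. Regression details normally belong in a statistical analysis plan, which is not at hand. Much of this stands, and it rules out four stronger readings that a reader might infer.

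- *The plan fixes a single pooled PPV.* It does not; it leaves the matching open.
- *The formula cannot use age-specific coverage.* It can, within strata or with incidence-weighted PPV, as step 4 shows. The bias comes from the choice of PPV.
- *VE will be inflated, so that even a useless vaccine looks protective.* The 39% figure needs 12-month coverage applied to younger infants, and section 9.4 plans supplementary data for exactly that limitation. The bias can go either way and vanishes with flat coverage.
- *The exact binomial interval is wrong.* It is a standard interval for PCV. If vaccination probability varies between cases, the variance of the vaccinated count is at most binomial, so the interval for PCV is conservative.

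The defence does not rescue the wording. The protocol states the estimator, the interval and the claim that adjustment is impossible and not needed, so this goes beyond omitted detail. The mitigations are optional, unclear in scope or without a range. Excluding people not offered the vaccine leaves age gradients among those who were.

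**Conclusion.** The concern holds in a limited form. The statements in sections 9.7.3 and 9.9 are unsupported, conflict with the protocol's own schedule and Table 3, and do not fit section 9.1. The estimator is stated without a rule linking cases to the planned age-specific coverage or combining strata.

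For a true VE of 60%, the resulting error is about -7 to +10 points in the moderate scenarios tabulated. It is about +16 points if three-dose status is pooled across the 12-month dose or 12-month coverage is applied to younger infants. All of these sizes rest on assumed coverage curves; only the case counts, dose ages, VE of 60% and flat 90% coverage come from the protocol. This should be corrected, but it does not show that the planned analysis must be biased.

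**What to change.** Specify that the primary screening estimate uses PPV matched to each case's age and birth cohort, and to period or region only where such coverage is available. One way is logistic regression of vaccinated (yes/no) among cases with offset logit(PPV) and VE = 1 - exp(intercept). Keep the crude formula with its exact interval as a check, or for single strata.

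Reconcile sections 9.1, 9.7.3 and 9.9. Replace the statements that control is impossible and not an issue with wording to this effect: confounding by age and cohort is controlled through matched coverage; individual-level confounders absent from the coverage data remain uncontrolled and are a limitation. State whether the stratified analyses by age apply to the screening method.

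The cost is slightly more analysis work, on coverage data by dose and age that section 9.4 already plans to obtain, and an interval that is model-based rather than exact when case counts are small.

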9.10 Other Aspects

Not applicable.

10. PROTECTION OF HUMAN SUBJECTS

Under the Data Protection Act covered by SI 2002/1438, no patient identifiable data will be transferred to a third party.

Details of the person reporting the case to PHE will not routinely be made available to the market authorisation holder (MAH).

10.1 Regulatory and Ethical Compliance

In 2001, PHE (formerly the Public Health Laboratory Service and Health Protection Agency) received approval from the Department of Health's Patient Information Advisory Group (now from the National Information Governance Board, NIGB) to continue the collection of personal's identification data for the surveillance, control and prevention of communicable diseases. This ongoing approval covers the routine meningococcal surveillance system. As such, any addition of vaccines will be notified to NIGB.

10.2 Informed Consent

The descriptive part of this observational study uses data routinely collected for national meningococcal surveillance by PHE. These data will be sent to GSK Vaccines S.r.l. in a pseudo-anonymised format containing no personal information; therefore, no informed consent will be required.

In additional to these data, the analytical part of the study collects history of vaccination data in order to link any occurring outcome of meningococcal disease to their potential exposure to the vaccine. For the screening method, pseudo-anonymised datasets containing no personal information will be used, for which no additional informed consent is required.

Simple demographics and vaccine history are both covered by NIGB's approval.

However, if we need to defer to the case-control design, eligible subjects will only be included in the study after providing written (witnessed, where required by law or regulation), IRB/IEC/REB-approved informed consent, or, if incapable of doing so, after such consent has been provided by a legally acceptable representative of the subject. In cases where consent is given by the subject's representative, the subject should be informed about the study to the extent possible given his/her understanding. If the subject is capable of doing so, he/she should indicate assent by personally signing and dating the written informed consent document or a separate assent form. Informed consent must be obtained before conducting any study-specific procedures (i.e. all of the procedures described in the protocol). The process of obtaining informed consent should be

GSK Vaccines S.r.l.		Observational Study Protocol V72_38OB
03 SEP 15 Version 3 Final	Confidential	Page 46 of 61

documented in the subject source documents. The consent form must be agreed to by GSK Vaccines S.r.l. and PHE before submission to the IRB/IEC/REB, and a copy of the approved version must be provided to all affiliations after IRB/IEC/REB approval.

10.3 Responsibilities of the Investigator and IRB/IEC/REB

NA, as this is a collaboration for provision of customised post-marketing surveillance reports of independently generated data to assist GSK Vaccines S.r.l. in meeting its regulatory commitment.

10.4 Protocol Adherence

The study in this protocol refers to the provision of customised post-marketing surveillance reports of independently generated data to assist GSK Vaccines S.r.l. in meeting its regulatory commitment. This collaboration makes use of routinely and independently generated national surveillance data, as approved by NIGB. There is no single protocol governing surveillance activities as the nature of vaccination schedule and surveillance requires a level of flexibility, though patient confidentiality is assured at all times.

11. MANAGEMENT AND REPORTING OF ADVERSE EVENTS

GSK Vaccines S.r.l. will undertake enhanced pharmacovigilance and a post-marketing observational safety study for the 4CMenB vaccine (see protocol V72_36OB), including the establishment of a pregnancy registry in the US (V72_82OB).

Individual cases of vaccine failure of 4CMenB vaccination during this study (V72_38OB) will not be reported as it is a vaccine effectiveness study. Data will be aggregated as per study design and reported to EMA as they become available every six months for the 3-year study duration as well as a final report 6 months after end of the study.

